## List of Abbreviations

° C	Degrees Celsius
A:G	Albumin:Globulin
ACE	Adverse Childhood Experiences Questionnaire
ADHD	Attention Deficit/Hyperactivity Disorder
AE	Adverse Event
AED	Automatic External Defibrillator
AESI	Adverse Event of Special Interest
ALT	Alanine Aminotransferase
AMI	Acute Myocardial Infarction
API	Active Pharmaceutical Ingredient
AST	Aspartate Aminotransferase
AUDIT	Alcohol Use Disorders Identification Test
BDI-II	Beck Depression Inventory-II
BLS	Basic Life Support
BMI	Body Mass Index
BP	Blood Pressure
BUN	Blood Urea Nitrogen
CAPS-4	Clinician-Administered PTSD Scale for DSM-4
CAPS-5	Clinician-Administered PTSD Scale for DSM-5
CBC	Complete Blood Count
%CDT	%Carbohydrate-deficient Transferrin
CMC	Chemistry Manufacturing and Control
CPGS	Chronic Pain Grade Scale
CRA	Clinical Research Associate
C-SSRS	Columbia-Suicide Severity Rating Scale
DDIS	Dissociative Disorders Interview Schedule
DID	Dissociative Identity Disorder
dIGPP	Cohen's d Independent Groups Pre-test Post-test
DMF	Drug Master File
DSM-5	Diagnostic and Statistical Manual of Mental Disorders, 5 th edition
DSP-I	Dissociative Subtype of PTSD Interview
DUDIT	Drug Abuse Disorders Identification Test
EAT-26	Eating Attitudes Test
ECG	Electrocardiogram
eCRF	Electronic Case Report Form
ECT	Electroconvulsive Therapy
ED	Emergency Department
EDC	Electronic Data Capture
EMDR	Eye Movement Desensitization and Reprocessing
EMS	Emergency Medical Services
ePRO	Electronic Participant Reported Outcome
EQ-5D-5L	EuroQol Five Dimensions – Five Levels Questionnaire
FDA	Food and Drug Administration
GCP	Good Clinical Practice
GMP	Good Manufacturing Practice
HCV	Hepatitis C Virus
HIV	Human Immunodeficiency Virus
HIPAA	Health Insurance Portability and Accountability
HPA	Hypothalamic-pituitary-adrenal
HPMC	Hydroxypropyl Methylcellulose

HPQSF	Health and Work Performance Absenteeism and Presenteeism Short Form
IASC	Inventory of Altered Self-Capacities
IB	Investigator's Brochure
ICD	International Classification of Disease
ICF	Informed Consent Form
ICH	International Conference on Harmonisation
IND	Investigational New Drug
IP	Investigational Product
IPF	Inventory of Psychosocial Functioning
IR	Independent Rater
IRB	Institutional Review Board
ISF	Investigator Site File
ITT	Intent-to-Treat
IUD	Intrauterine Device
IUS	Intrauterine Hormone-releasing System
kg	Kilogram
LEC-5	Life Events Checklist
LTFU	Long-term Follow-up
MAPS	Multidisciplinary Association for Psychedelic Studies
MAOI	Monoamine Oxidase Inhibitor
MCH	Mean Corpuscular Hemoglobin
MCHC	Mean Corpuscular Hemoglobin Concentration
MCV	Mean Corpuscular Volume
MDMA	3,4-methylenedioxymethamphetamine
MedDRA	Medical Dictionary for Regulatory Activities
mg	Milligram
m ITT	Modified Intent-to-Treat
mmHg	Milligrams of Mercury
MMRM	Mixed Model Repeated Measure
MPBC	MAPS Public Benefit Corporation
ms	Millisecond
PCL-5	PTSD Checklist for DSM-5
PTCA	Percutaneous Transluminal Coronary Angioplasty
PTSD	Posttraumatic Stress Disorder
RACT	Risk Assessment and Categorization Tool
RBC	Red Blood Cell
RDW	Red Cell Distribution Width
SAE	Serious Adverse Event
SCID-5-PD	Structured Clinical Interview for DSM-5 Personality Disorders
SCID-5-SPQ	SCID-5 Self-report Personality Questionnaire
SCS	Self-compassion Scale
SDS	Sheehan Disability Scale
SGOT	Serum Glutamic Oxaloacetic Transaminase
SNRI	Serotonin-norepinephrine Reuptake Inhibitor
SPGT	Serum Glutamic Pyruvic Transaminase
SRNU	Self-reported Nicotine Use
SSR	Sample size re-estimation
SSRI	Selective serotonin reuptake inhibitor
SUBJID	Subject Identifier
TAS-20	Toronto Alexithymia Scale
TEAE	Treatment Emergent Adverse Event
TSH	Thyroid-stimulating Hormone

UFEC	Utilization of Facility-based and Emergent Care
U.S.	United States
VA	U.S. Department of Veterans Affairs
VAS	Visual Analog Scale
WBC	White Blood Cell
WHO	World Health Organization
WHO DDE	WHO Drug Dictionary Enhanced™

## 1.0 Definitions of Terms

*Categorical data:* refers to discrete (indivisible) variables, such as gender or ethnicity; data will be presented as total numbers of each category as needed to describe the sample

*Completers:* are defined as participants who complete all three planned experimental sessions and the PCL-5 outcome assessment at Visit 16.

*Descriptive data:* includes mean, median, standard deviation, minimum, and maximum of numerical data used as needed to describe the sample

*Difference scores:* consist of scores computed by subtracting one value from another, as subtracting Baseline from follow-up score, used to test for differences between and within groups to determine change as a function of experimental treatment over time

*Dropouts:* are defined as participants who withdraw consent due to any reason after dosing and no longer participate in the study, i.e. no further contact with investigators or site staff.

*Efficacy:* type of analysis used to assess therapeutic effects or benefits

*Exploratory analyses:* inferential or descriptive analysis of the data to determine trends that might lead to hypotheses for further study

*Frequency listing:* tabular listing of numbers and/or percentages of events used as needed to describe the sample or data characteristics

*Outcome measures:* primary and secondary study measures that are used to test the study hypotheses

*Post-dosing Early Terminators:* are defined as participants who discontinue study treatment but continue to participate in study evaluations and outcome assessments.

*Pre-dosing Early Terminators:* are defined as participants who discontinue participation after enrollment but before randomization during the Preparatory Period and never receive study drug.

*Process measures:* study measures or qualitative observations collected during the study that may increase depth of understanding of the condition and treatment, although not necessarily related to safety or efficacy

*Protocol deviation:* event that represents significant divergence from the intended study design as described in the protocol

*Safety:* assessment of indicators of potential risks and adverse events

*Safety measures:* study measures that assess safety of the Investigational Product (IP), such as heart rate monitoring, blood pressure, body temperature

*Study design:* all elements of a research project that define the study question, experimental methods, study procedures including blinding, measurement techniques, data workflow, and statistical analysis

*Tabular listing:* list of each variable or item for each individual participant either in total or by treatment group in a table format

## **2.0 Introduction**

This document contains a Statistical Analysis Plan (SAP) for MAPPUSX “A Multi-Site Open-Label Safety Extension Study of Manualized MDMA-Assisted Therapy for the Treatment of Participants with Posttraumatic Stress Disorder.”

The Multidisciplinary Association for Psychedelic Studies (MAPS) is a non-profit research and educational organization working as a clinical trial sponsor to obtain marketing approval for the prescription use of 3,4-methylenedioxymethamphetamine (MDMA) as an adjunct to therapy in patients with posttraumatic stress disorder (PTSD). Controlled Phase 1 studies, nonclinical studies, and investigator-initiated studies formed the basis for the Clinical Development Program of MDMA under Investigational New Drug (IND) #063384. MAPS-sponsored studies are implemented through MAPS’ wholly owned subsidiary and delegate, the MAPS Public Benefit Corporation (MPBC).

This multi-site open-label safety extension study of manualized MDMA-assisted therapy for the treatment of participants with PTSD will be conducted in N≈100 participants, by invitation only.

The treatment consists of a flexible dose of MDMA, followed by a supplemental dose unless tolerability issues emerge administered with manualized therapy in three open-label approximately monthly Experimental Sessions. This Treatment Period is preceded by three Preparatory Sessions. During the Treatment Period, each Experimental Session is followed by three Integrative Sessions of non-drug therapy. Experimental Sessions are followed by an overnight stay; a sub-study will assess feasibility of Experimental Sessions without an overnight stay. The Primary Outcome measure, the change in PCL-5 (PTSD Checklist for DSM5) from Visit 3 is assessed at Visit 16. An independent Data Monitoring Committee (DMC) will review safety data as described in the DMC charter and at any time a Serious Adverse Reaction (SAR) occurs.

## **3.0 Study Objectives**

### **3.1 Primary Objective**

The primary objective of this study is to evaluate the effectiveness of MDMA-assisted therapy for PTSD, as measured by the reduction in PCL-5 total score from Visit 3 to Visit 16.

### **3.2 Secondary Objective**

The key secondary objective of this study is to evaluate the effectiveness of MDMA-assisted therapy for PTSD in functional impairment, as measured by the mean change in Sheehan Disability Scale (SDS) item scores from Visit 3 to Visit 16.

### **3.3 Safety Objectives**

The overall safety objective is to assess severity, incidence and frequency of Adverse Events (AEs), Treatment Emergent AEs (TEAEs), AEs of Special Interest (AESIs), and Serious Adverse Events (SAEs), concomitant medication use, suicidal ideation and behavior, and vital signs to support the package insert for MDMA-assisted therapy. The following safety objectives will evaluate the safety of MDMA-assisted therapy:

1. Assess incidence of AEs during Experimental Sessions that may be indicative of a medical complication of the Investigational Medicinal Product (IMP) such as clinical signs and symptoms of chest pain, shortness of breath, or neurological symptoms or any other signs or symptoms that prompt additional vital sign measurements
2. Assess incidence of AEs by severity
3. Assess incidence of TEAEs by severity
4. Assess incidence of TEAEs by severity reported during an Experimental Session, 1 day, and 2 days after IMP administration
5. Assess incidence of AESIs, defined as AEs specified in the protocol related to cardiac function, suicidality, and abuse liability
6. Assess incidence of AEs by severity categorized as leading to discontinuation of IMP, resulting in death or hospitalization, and continuing at Study Termination
7. Assess incidence of SAEs
8. Assess incidence of concomitant medications taken during an Experimental Session, 1 day, and 2 days after IMP administration
9. Assess incidence of psychiatric concomitant medications taken during the Treatment Period
10. Assess incidence of positive or serious suicidal ideation and positive suicidal behavior assessed with the Columbia Suicide Severity Rating Scale (C-SSRS)
11. Assess changes in blood pressure (BP), heart rate, and body temperature from pre-IMP administration to end of each Experimental Session

### **3.4 Exploratory Objectives**

These objectives may be explored to characterize participants receiving MDMA-assisted therapy to support the primary objective:

1. Explore the effect of presence of secondary traumatic stressors identified on the Life Events Checklist (LEC-5) on the PCL-5 total severity analysis
2. Explore differences from Visit 3 to Visit 16 in:
  - a. Depression (BDI-II)
  - b. Chronic pain (CPGS)
  - c. Quality of life (EQ-5D-5L)
  - d. Nicotine use (SRNU)
  - e. Eating habits (EAT-26)
  - f. Workplace productivity (HPQSF)
3. Explore differences from Screening to Visit 16 in alcohol use (AUDIT) and drug use (DUDIT)

## **4.0 Measures**

### **4.1 Primary Measure**

- PCL-5 (PTSD Checklist)

### **4.2 Secondary Outcome Measure**

- Sheehan Disability Scale (SDS)

### **4.3 Safety Measures**

- Columbia Suicide Severity Rating Scale (C-SSRS)
- Adverse Events

- Treatment-emergent Adverse Events
- Serious Adverse Events
- Adverse Events of Special Interest
- Concomitant medication use
- Vitals signs during MDMA sessions

#### 4.4 Exploratory Measures

- Life Events Checklist (LEC-5)
- Beck Depression Inventory II (BDI-II)
- Chronic Pain Grade Scale (CPGS)
- EuroQol Five Dimensions – Five Levels Questionnaire (EQ-5D-5L)
- Alcohol Use Disorders Identification Test (AUDIT)
- Drug Use Disorders Identification Test (DUDIT)
- Self-reported Nicotine Use (SRNU)
- EAT-26 (Eating Attitudes Test)
- HPQSF (Health and Work Performance Absenteeism and Presenteeism Short Form)
- Utilization of Facility-based and Emergent Care (UFEC)

#### 5.0 Study Design

**Table 1: Dose Regimen of MDMA**

Experimental Session	Initial Dose	Supplemental Dose*	Min-Max Cumulative Dose
1	80 mg	40 mg	80 to 120 mg
2	80 or 120 mg	40 or 60 mg	80 to 180 mg
3	80 or 120 mg	40 or 60 mg	80 to 180 mg
Total Cumulative Dose			240 to 480 mg

\* Unless contraindicated

**Table 2: Time and Events – Study Procedures**

	Screening Period (1 to 6 weeks)			Preparatory Period (At least 5 days, depending on medication tapering)			
	Screening			Preparatory			
Visit	Phone Screening	Screening	IR Screening	V0	V1	V2	V3
Visit Description	Phone Calls	In-person Visits & Labs	Telemedicine	Enrollment	Prep. 1	Prep. 2	Prep. 3
Visit Timing	Prior to Initial Screening	Over 7 to 42 days	2 to 9 days after initial eligibility met	2 to 14 days post IR Screening	0 to 14 days after V0	At least 2 days after V1 (depending on tapering)	Post V2 & Taper, 1 to 14 days before V4
Initial Phone Screen	✓						
Informed Consent	Send Copy	✓					
Follow-up Phone Screen	✓						
Assess Eligibility	✓	✓	✓	✓	✓	✓	✓
Medical/Psychiatric History	✓ A	✓			✓	✓	✓
Past/Current Medication & Adherence	✓	✓		✓	✓	✓	✓
Weight		✓					
Resting Vitals		✓					
Physical Exam		✓					
ECG & Rhythm Strip		✓					
Clinical Lab Tests		✓					
Drug Screen		✓					✓
Pregnancy Screen		✓					✓
Enter Participant in eCRF		✓					
Independent Rater Assessment			✓				
Medication Taper				✓	✓	✓	
Study Enrollment				✓			
All AEs B				✓	✓	✓	✓
90-min Preparatory Session					✓	✓	✓
Phone Call Follow-up C						✓	
Measures (ePRO or Clinician-Administered) D		✓	✓		✓	✓	✓

A At Screening, collect data on previous hospitalizations and healthcare utilization. Request participants to obtain medical/psychiatric records generated since the end of the parent study to bring to the in-person screening

B All Adverse Events (AEs) includes collecting Serious Adverse Events, AEs of Special Interest, AEs of Psychiatric Status, AEs requiring medical advice or attention, AEs that indicate withdrawal of a participant, and all other AEs

C If needed, call participant to confirm medication tapering and stabilization is complete prior to Visit 3

D Refer to [Table 6: Time and Events-Measures](#) for details

	Treatment Period 8 to 20 weeks												
	Treatment 1				Treatment 2				Treatment 3				Study Termination
Visit	V4	V5	V6	V7	V8	V9	V10	V11	V12	V13	V14	V15	V16
Visit Description	Exp. 1	Int. 1.1	Int. 1.2 F	Int. 1.3 F	Exp. 2	Int. 2.1	Int. 2.2 F	Int. 2.3 F	Exp. 3	Int. 3.1	Int. 3.2 F	Int. 3.3 F	Study Termination
Visit Timing	1 to 14 days after V3	Morning after V4	10 to 18 days after V4	At least 2 days after V6; 1 to 14 days before V8	21 to 56 days after V4	Morning after V8	10 to 18 days after V8	At least 2 days after V10; 1 to 14 days before V12	21 to 56 days after V8	Morning after V12	10 to 18 days after V12	At least two days after V14	24 to 32 days after V12
Past/Current Medication & Adherence	✓	✓	✓	✓	✓	✓	✓	✓	✓	✓	✓	✓	✓
Drug Screen	✓				✓				✓				
Pregnancy Screen	✓				✓				✓				
All AEs A	✓	✓	✓	✓	✓	✓	✓	✓	✓	✓	✓	✓	✓
Container Assignment B	✓				✓				✓				
Administer IMP	✓				✓				✓				
8-hour Exp. Session	✓				✓				✓				
BP, Pulse, Temperature	✓ C				✓ C				✓ C				✓ D
Potential Overnight Stay	✓				✓				✓				
90-min Integrative Session		✓	✓	✓		✓	✓	✓		✓	✓	✓	
Phone Call Follow-up E		✓				✓				✓			
Weight													✓
Blood Draw (CRP)													✓
Measures (ePRO or Clinician-Administered G )	✓	✓ E	✓	✓	✓	✓ E	✓	✓	✓	✓ E	✓	✓	✓

A All Adverse Events (AEs) includes collecting Serious Adverse Events, AEs of Special Interest, AEs of Psychiatric Status, AEs requiring medical advice or attention, AEs that indicate withdrawal of a participant, and all other AEs

B Obtain container assignment 24 to 48 hours prior to each Experimental Session

C During Experimental Sessions, vitals are measured before Investigational Product administration, immediately before the supplemental dose is administered (or would be, if supplemental dose not given), and approximately 8 hours after initial dose, and as needed

D At Study Termination, only blood pressure needs to be measured

E 14 days of phone call follow-up: every other day after the Experimental Session; includes C-SSRS administration and AE collection

F All Integrative Sessions must be at least 2 days apart

G Refer to [Table 6: Time and Events-Measures](#) for details

Visit Description	Visit #	Screening		Preparatory Period			Treatment 1				Treatment 2				Treatment 3				Study Termination
		Screening	IR Screening	V1	V2	V3	V4	V5	V6	V7	V8	V9	V10	V11	V12	V13	V14	V15	V16

## 6.0 Randomization and Blinding

This is an open-label study with no randomization or blinding.

## 7.0 Sample Size and Power Considerations

This is a one-arm open-label study. Thus, no power nor sample size calculations are required.

## 8.0 Analyses

Every effort will be made to ensure complete, accurate and timely data collection and to avoid missing data, to ensure the completeness of the data which can impact the integrity and accuracy of the final study analysis. The statistical analyses will be reported using summary tables, figures, and data listings. All analyses and tabulations will be performed using SAS® Version 9.4 or higher, and S-PLUS. In general, nominal variables will be described in terms of frequencies and percentages. Ordinal and non-normal continuous variables will be described using sample median and range.

Approximately normally distributed continuous variables will be described using sample mean and standard deviations and analyzed by parametric statistical tests. Otherwise, Wilcoxon rank-sum tests will be used. Categorical variable will be displayed by counts and percentages and analyzed by chi-squared tests. Except for the primary efficacy analysis, all statistical tests will be two-sided and a difference resulting in a p-value of less than or equal to 0.05 will be considered statistically significant. All p-values will be rounded to and displayed in four decimals. If a p-value less than 0.0001 occurs it will be shown in tables as <0.0001. Data not subject to analysis according to this plan will not appear in any tables or graphs, but will be included in the data listings. Selected results may be presented graphically using standard graphical software.

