### 8.7.1 Primary Effectiveness Analysis

The primary analysis of the effectiveness of MDMA-assisted psychotherapy will be made using a Mixed Model Repeated Measure (MMRM) model to assess changes in PCL-5 scores throughout the study period from Baseline (Visit 3) through Visit 16. Baseline covariates (baseline PVL-5, age, gender, ethnicity, index trauma, complexity and severity of trauma, diagnosis of comorbid depression, diagnosis of comorbid Axis 2 diagnosis, adverse childhood experiences collected in the parent study) may be assessed for inclusion in the final model with an alpha level set at 0.05.

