### 8.7.3 Exploratory Analyses

Post-hoc exploratory analyses not identified in this SAP may be performed to further examine the study data. In particular, MMRM models, linear regression, and/or ANCOVA models may be utilized to analyze the effect of MDMA in conjunction with psychotherapy on the following exploratory endpoints:

- Presence of secondary traumatic stressors identified on the Life Events Checklist (LEC-5) on the PCL-5 total severity analysis
- Depression (BDI-II)
- Chronic pain (CPGS)
- Quality of life (EQ-5D-5L)
- Nicotine use (SRNU)
- Eating habits (EAT-26)
- Workplace productivity (HPQSF)
- Alcohol use (AUDIT)
- Drug use (DUDIT)

These analyses will be clearly identified as exploratory in the final clinical study report.

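### SAP 8.0 names only independent-sample tests (rank-sum, chi-squared) for non-normal and categorical data, although the one-arm study's exploratory objectives compare the same participants over time

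*SAP*

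**What the plan says.** SAP 8.0 gives the plan's only general rule for choosing a test. Approximately normal variables get parametric tests of no stated kind. For the rest: "Otherwise, Wilcoxon rank-sum tests will be used. Categorical variable will be displayed by counts and percentages and analyzed by chi-squared tests". Outside the primary analysis, tests are two-sided at 0.05.

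The design has no comparison group. SAP 6.0 states: "This is an open-label study with no randomization or blinding". SAP 7.0 adds: "This is a one-arm open-label study".

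The exploratory objectives in SAP 3.4 concern change within participants. For BDI-II, CPGS, EQ-5D-5L, SRNU, EAT-26 and HPQSF the wording is "Explore differences from Visit 3 to Visit 16 in"; for AUDIT and DUDIT the comparison runs from Screening to Visit 16. SAP 1.0 defines difference scores as "used to test for differences between and within groups to determine change as a function of experimental treatment over time", but names no test for them.

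SAP 8.7.3 adds that "MMRM models, linear regression, and/or ANCOVA models may be utilized to analyze the effect of MDMA in conjunction with psychotherapy" on these endpoints. The primary PCL-5 analysis (SAP 8.7.1) is an MMRM, and the SDS (SAP 8.7.2) is handled similarly.

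**The concern.** A rank-sum test needs two independent samples, and an ordinary chi-squared test needs independent observations. A before-and-after comparison in one arm supplies neither. A rank-sum test cannot be run on a single column of difference scores. It can be run only by treating the two visits as if different people had attended them, which discards the pairing. The same holds for a chi-squared test that sets one visit's counts against the other's.

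No signed-rank, sign, McNemar or marginal-homogeneity test appears in either document. An analyst who tests a change on a skewed exploratory scale without a model therefore has one written instruction, and it does not fit the data. At stake is a small real change on an exploratory scale being reported as not significant.

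**Working it through.** The plan has no power or sample size calculation to reproduce: SAP 7.0 says none is required, and Protocol 13.1 says the sample size has no statistical basis.

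**Inputs from the documents.** About 100 participants (SAP 2.0); two-sided 0.05 (SAP 8.0); one arm (SAP 7.0).

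**Assumed inputs, not in the documents.** Within-person correlation ρ of 0.3 / 0.5 / 0.7; changes of 0.3 and 0.5 of the single-visit SD; equal variances; bivariate normal data with both visits complete unless stated.

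**Step 1: true size of the rank-sum test on paired data.** The Spearman correlation is r_s = (6/π)·asin(ρ/2). The pairing shrinks the null variance by the factor (1 − r_s), so the true size is 2·[1 − Φ(1.96/√(1 − r_s))].

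| ρ | r_s | 1.96/√(1 − r_s) | true size |
|---|---|---|---|
| 0.3 | 0.288 | 2.32 | 2.0% |
| 0.5 | 0.483 | 2.72 | 0.6% |
| 0.7 | 0.683 | 3.48 | 0.05% |

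Simulation (20,000 runs) gives 1.97% / 0.66% / 0.06%. The signed-rank test on the same data holds 5.1% / 4.9% / 4.7%.

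**Step 2: power at 0.3 SD.** A normal approximation for tests of means shows the mechanism.
- Unpaired: Φ((0.3·√(100/2) − 1.96)/√(1 − ρ)) = Φ(0.161/√(1 − ρ)) = 58% / 59% / 62%.
- Paired: Φ(0.3·√(100/(2(1 − ρ))) − 1.96) = Φ(0.58) / Φ(1.04) / Φ(1.91) = 72% / 85% / 97%.

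Simulation of the rank tests themselves gives about 55% / 56% / 57% for rank-sum and 69% / 82% / 96% for signed-rank. The paired test gains from the correlation; the unpaired test hardly does.

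**Step 3: power at 0.5 SD.** The same formulas give Φ(1.576/√(1 − ρ)) = 97% / 98.7% / 99.8% unpaired, and Φ(2.27) / Φ(3.04) / Φ(4.50) = 98.8% / 99.9% / 100% paired. Simulated rank-sum power is about 96% / 98% / 99.6%; signed-rank is 98–99% / 99.7–99.8% / 100%. The gap has nearly closed.

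**Step 4: fewer pairs and skewed data, at 0.3 SD.**
- If the 7.5% Phase 2 dropout in Protocol 1.2.4 applied, 100 × (1 − 0.075) = 92.5, or 92 pairs. Rank-sum power is 51% at each correlation, against 65% / 80% / 95%.
- On a skewed integer scale with a floor at zero and 100 pairs, power is 52–53% against 60% / 72% / 89%. In this case the correlation and the shift apply to the underlying normal scale.

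**Step 5: categorical data.** For a binary item moving from an assumed 50% to 35%, with latent correlation 0.3 / 0.5 / 0.7 and 100 pairs (4,000 runs):
- Size: chi-squared 3.4% / 1.9% / 0.5%; McNemar 5.0% / 4.6% / 5.0%.
- Power: chi-squared 59% / 61% / 62%; McNemar 66% / 75% / 85%.

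**The case against.** The strongest reply is that no planned analysis has to use this default. PCL-5 and SDS go to a model. SAP 8.7 provides descriptive statistics for all endpoints. The exploratory objectives are optional, and SAP 8.7.3 lists each of those endpoints with models that can respect the pairing. C-SSRS results and vital signs are summarised descriptively. Unspecified parametric tests could include a paired t-test. On this view SAP 8.0 is general wording that names the wrong Wilcoxon test, and a competent analyst would see that.

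Most of this stands and limits the severity. It does not remove the point: SAP 8.7.3 is permissive and never says that its models replace the SAP 8.0 rule. It is also fair that the loss of power matters only for small changes, as Step 3 shows, and that the plan names no categorical change endpoint to be tested.

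Three stronger readings go beyond the documents.

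- A reader might infer that the main results are compromised. They are not: SAP 8.7.1 and 8.7.2 send PCL-5 and SDS to a repeated-measures model.
- A reader might infer more false positives. With positive within-person correlation the error goes the other way. Only a negative correlation would push the size above 5%, which would be unusual for repeated scores on one scale.
- A reader might join this to the sentence that primary-model covariates "may be assessed for inclusion in the final model with an alpha level set at 0.05", and to SAP 8.0 leaving the primary test's sidedness unstated, and conclude that the primary model needs redesign. The choice of default tests supports no such conclusion. Covariate selection is a separate question, and the primary objective already gives the direction: "as measured by the reduction in PCL-5 total score from Visit 3 to Visit 16".

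**Conclusion.** The point holds, and it is minor. The default tests named for non-normal and categorical data do not fit within-participant comparisons in a one-arm study, and no paired alternative is named. The exposure is confined to exploratory changes that are tested without a SAP 8.7.3 model. There, a nominal 5% rank-sum test has a true size of roughly 2% down to 0.05%. At a 0.3 SD change it gives up about 14, 26 and 39 percentage points of power (69 − 55, 82 − 56, 96 − 57). At 0.5 SD the loss is about 3 points or less.

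The sizes rest on assumed correlations and effects, since the documents give neither. The direction, conservative, rests on the within-person correlation being positive. Rank-sum and chi-squared tests remain valid between separate participants.

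**What to change.** In SAP 8.0:

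- For within-participant comparisons not analysed by a model, specify the paired t-test, or the Wilcoxon signed-rank test where normality is doubtful, on the difference scores already defined in SAP 1.0.
- For any categorical change that is tested, specify McNemar's test, or a marginal-homogeneity test for more than two categories.
- Keep rank-sum and chi-squared only for comparisons between separate participants, for example those with and without a stressor reported on the LEC-5.
- State that these defaults apply where no SAP 8.7.3 model is used.

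The cost is SAP wording and small program changes. No new data or participants are needed. Protocol 13.2 names none of these default tests, so it needs no matching edit.
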